#### Hypothesis Testing

The null and alternative hypotheses for CLUE comfort non-inferiority of the Test lens relative to the Control lens are as follows:

$$\begin{array}{l} H_0: \ \beta_1 \le -5 \\ H_A: \ \beta_1 > -5 \end{array}$$

Non-inferiority will be declared if the lower bound of the 2-sided 95% credible interval of the difference between the Test lens and the Control lens is greater than -5, i.e.,  $P(\beta_1 > -5) \ge 0.975$ .

#### Vision Satisfaction in Bright Lighting

The response set will first be reversed in order to appropriately analyze the data in order to provide the odds ratio of having a higher rating with the Test compared to the Control lens. Vision satisfaction in bright lighting at the 2-week follow-up evaluation will be analyzed using a Bayesian multinomial model for ordinal data. The regression model will include lens type as the only fixed effect. Clinical site will be included as a random effect. Other subject characteristics such as age, gender, race and iris category will be included when appropriate.

The Model:

Let  $y_{ijk} = (y_{ijk1}, y_{ijk2}, y_{ijk3}, y_{ijk4}, y_{ijk5})$  denote the rating for the  $k^{th}$  subject, from the  $j^{th}$  site, assigned to the  $i^{th}$  study lens. Possible values of  $y_{ijk}$  are 1 if the subject rating of vision satisfaction in bright lighting are X and 0 otherwise (x=1 for Strongly Agree and X=5 for Strongly Disagree, respectively). The likelihood is constructed as follows:

$$\begin{split} y_{ijk} \sim & \text{Multinomial} \ (P_{ijk1}, \ P_{ijk2}, P_{ijk3}, P_{ijk4}, P_{ijk5}); \\ & P_{ijk1} = \gamma_{ijk1} \\ & P_{ijkX} = \gamma_{ijkX} \cdot \gamma_{ijk(X-1)} \ 2 \leq X \leq 4 \\ & P_{ijk5} = 1 - \sum_{X=1,.4} P_{ijkX} \\ & \text{Logit}(\gamma_{ijkX}) = \theta_X + \beta_1 Lens_i + \delta_j \end{split}$$

Where  $\theta_x$  is the intercept for levels X=1,2,3,4, We assume the random clinical site effects are i.i.d as  $\delta_j \sim N(0, \sigma_{site}^2)$  for j=1, 2, 3, 4, 5, 6(site).

In this model, we define  $Lens_i=0$  for the Control lens and  $Lens_i=1$  for the Test lens.

Independent non-informative N(0, 1000) priors for the regression coefficients  $\beta_1$ . For the variance of random effect of  $\sigma_{site}^2$  an independent non-informative conjugate prior, inverse-gamma(0.001, 0.001) will be used. For  $\theta_x$ , we are considering the following priors

 $\begin{aligned} &\pi 0(\theta 1) \sim N(0,100) \\ &\pi 0(\theta 2|\; \theta 1) \sim N(0,100)I(\theta > \theta 1) \\ &\pi 0(\theta 3|\; \theta 2) \sim N(0,100)I(\theta > \theta 2) \\ &\pi 0(\theta 4|\; \theta 3) \sim N(0,100)I(\theta > \theta 3) \end{aligned}$ 

For the variance of random effects independent non-informative normal priors will also be used;  $\sigma_{site}^2 \sim inverse-gamma(0.001, 0.001)$ . The Metropolis sample algorithm as implemented in the SAS/Stat MCMC Procedure will be used to estimate the posterior distributions of the unknown parameters. Inferences will be made based on the posterior credible interval for the relevant parameters.

If few subjects reported in category levels disagree and strongly disagree (less than 5%); the levels will be collapsed into one category level.

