7.2. Detailed Study Procedures

VISIT 1

The subjects must present to Visit 1 wearing their habitual contact lenses.

	Visit 1: Screening			
Step	Procedure	Details		
1.1	Statement of Informed Consent	Each subject must read, understand, and sign the Statement of Informed Consent before being enrolled into the study. The Principal Investigator or his/her designee conducting the informed consent discussion must also sign the consent form.		
r.		Note : The subject must be provided a signed copy of this document.		
1.2	Demographics	Record the subject's date of birth, gender, race and ethnicity.		
1.3	Medical History and Concomitant Medications	Questions regarding the subjects' medical history and concomitant medications.		
1.4	Habitual Lenses	Questions regarding the subject's habitual lens type and parameters.		
1.5	Eligibility after Screening	All responses to Screening Inclusion Criteria questions must be answered "yes" and all responses to Exclusion Criteria must be answered "no" for the subject to be considered eligible.		

	Visit 1: Screening			
Step	Step Procedure Details			
		If the subject is deemed to be ineligible after screening, proceed to Final Evaluation and complete Subject Disposition. Refraction and Biomicroscopy forms are not required.		

	Visit 1: Baseline			
Step	Procedure	Details		
1.6	Baseline Questionnaire	The subject will respond to the CLUE Baseline Questionnaire.		
1.7	Entrance Visual Acuity	Record the distance Snellen visual acuity (OD, OS, and OU) to the nearest letter with their habitual contact lens correction in place. Subjects must read the smallest line until at least 50% of the letters are read incorrectly.		
1.8	Remove Habitual Lens	The subject's habitual lenses will be removed and stored in their own lens case. If they forgot to bring their lens case, one will be provided to them.		
1.9	Iris Color	The investigator will record the subject's iris color based on the scale provided.		
1.10	Keratometry	Record the keratometry readings OD and OS in diopters. This can come from any appropriate instrument so long as the same instrument is used at the Final Evaluation.		
1.11	Subjective Sphero- cylindrical Refraction	Complete subjective spherocylindrical refraction and record the resultant distance visual acuity (OD, OS, and OU) to the nearest letter. Best corrected distance visual acuity (BVA) must be 20/25+3 or better in each eye.		

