### **CLUE Overall Comfort**

CLUE Comfort scores will be analyzed using a Bayesian normal random-effects model to compare the Test and Control lenses at the 2-week follow-up evaluation. The regression model will include baseline CLUE comfort scores and lens type as fixed effects. Clinical site will be included as random effects. Other subject characteristics such as age, gender, race and iris category will be included as fixed covariates when appropriate.

The Model:

Let  $y_{ijk}$  denote the CLUE Comfort score for the  $k^{th}$  subject at the  $j^{th}$  site, assigned to the  $i^{th}$  lens. The likelihood for  $y_{ijk}$  is constructed as follows:

$$y_{ijk} \sim N(\mu_{ijk}, \sigma_{ijkl}^2)$$

Where

$$\mu_{ijkl} = \mu_0 + \beta_1 Lens_i + \beta_2 baseline + \gamma_j$$

In this model, we define  $Lens_i=0$  for the Control lens and  $Lens_i=1$  for the Test lens. So  $\beta_1$  stands for the difference between the Test and Control lens with respect to CLUE comfort; A positive  $\beta_1$  indicates the Test performed better than the Control.

We assume random site effects are independent and identically distributed (i.i.d) as  $\gamma_j \sim N(0, \sigma_{sits}^2)$  for site for j=1, 2, 3, 4, 5, 6 (site).

For the  $\beta$  coefficients, independent non-informative priors N(0, 1000) will be used. For the variance of random effect of  $\sigma_{site}^2$  an independent non-informative conjugate prior, inverse-gamma(0.001, 0.001) will be used. Starting values for the mean and variance of CLUE scores will be 60 and 400 (since standard deviation of CLUE is normalized to be 20), respectively. The Metropolis sampler algorithm as implemented in the SAS/STAT MCMC 14.2 procedure will be used to estimate the posterior distribution of the unknown parameters. Inferences will be made based on the 95% posterior credible intervals for relevant parameters.

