## **CLUE Overall Quality of Vision and Handling**

CLUE Overall Quality of Vision and Handling will be analyzed using the same statistical method described for CLUE Overall Comfort.

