Vision Satisfaction in Bright Lighting

```
PROC MCMC DATA =ads VS SEED=20181019 nbi =100000 nmc =500000 thin=100
DIAG=ALL OUTPOST=simout DIC PLOTS(SMOOTH FRINGE) = ALL
MCHISTORY=BRIEF PROPCOV=QUANEW STATS=ALL STATS(ALPHA=(0.05)
PERCENTAGE = (2.5 50 97.5))
plots(smooth)=ALL MONITOR=(_parms_OR);
```

ARRAY theta[4] theta1-theta4; ARRAY gamma[4] gamma1-gamma4;

PARMS theta1-theta4 beta0 0 beta1 0 beta2 0 beta3 0; PARMS s2g 1;

PRIOR beta: ~ NORMAL(0,VAR=1000); PRIOR theta1 ~ NORMAL(0,VAR=100); PRIOR theta2 ~ NORMAL(0,VAR=100,lower=theta1); CR-6305, Statistical Analysis Plan Version 1.0

```
PRIOR theta3 ~ NORMAL(0,VAR=100,lower=theta2);
PRIOR theta4 ~ NORMAL(0,VAR=100,lower=theta3);
PRIOR s2g ~ IGAMMA(.01, s =.01);
```

```
RANDOM Gamma site ~ NORMAL(0, VAR = s2g) SUBJECT=SITEID;

mu = beta0 + beta1*TRTAN + beta2*age + beta3*sexn + Gamma_site;

DO j = 1 to 4;

gamma[j] = logistic(theta[j] + mu);

END;

pi1 = gamma1;

pi2 = gamma2 - gamma1;

pi3 = gamma3 - gamma2;

pi4 = gamma4 - gamma3;

pi5 = 1 - sum(of pi1-pi4);
```

```
llike = logmpdfmultinom(of y1-y5, of pi1-pi5);
MODEL DGENERAL(llike);
```

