#### **BEGINNODATA;**

```
array gammac[5];
  array gammat[5];
  array pc[5];
  array pt[5];
  DO i = 1 to 5;
   gammac[i] = logistic(theta[i] + beta0 + 0.5*beta3);
   gammat[i] = logistic(theta[i] + beta0 + beta1 + 0.5*beta3);
  END;
 pc1 = gammac1;
 pc2 = gammac2 - gammac1;
 pc3 = gammac3 - gammac2;
 pc4 = gammac4 - gammac3;
 pc5 = 1 - sum(of pc1-pc4);
 pt1 = gammat1;
 pt2 = gammat2 - gammat1;
 pt3 = gammat3 - gammat2;
 pt4 = gammat4 - gammat3;
 pt5 = 1 - sum(of pt1-pt4);
 p2box c = pc1 + pc2;
 p2box t = pt1 + pt2;
 diff = p2box t - p2box c;
ENDNODATA:
RUN;
```

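### The bright-light primary model leaves out baseline CLUE information that the other CLUE models use, which costs efficiency on a must-pass test but causes no bias

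*SAP*

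**What the plan says.** SAP 10.1 (Vision Satisfaction in Bright Lighting) specifies a Bayesian cumulative-logit model for the five-level item with a random site effect: "The regression model will include lens type as the only fixed effect". It then allows further terms: "Other subject characteristics such as age, gender, race and iris category will be included when appropriate". Baseline is not among them. The code in SAP 14.1 fits "mu = beta0 + beta1*TRTAN + beta2*age + beta3*sexn + Gamma_site", so age and sex enter but baseline does not. The group probabilities are then computed at fixed covariate values, for example "gammac[i] = logistic(theta[i] + beta0 + 0.5*beta3" for Control. Sex is set to one half and the age term is left out.

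The other CLUE endpoints are treated differently. For comfort: "The regression model will include baseline CLUE comfort scores and lens type as fixed effects". For the secondary endpoints, SAP 10.2 says: "CLUE Overall Quality of Vision and Handling will be analyzed using the same statistical method described for CLUE Overall Comfort".

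A baseline measurement is taken. Protocol 7.2, step 1.6 reads: "The subject will respond to the CLUE Baseline Questionnaire". SAP 2.4 requires baseline information before randomisation. The bright-light item (V015_1) is itself a CLUE item (SAP 3.1). SAP 4.1 requires every primary hypothesis to be met. For this one, the lower 95% credible limit of the Test minus Control difference in the proportion agreeing or strongly agreeing must exceed -0.10. No reason is given for leaving baseline out.

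**The concern.** Satisfaction with vision in the habitual lenses plausibly predicts satisfaction two weeks later. A prespecified baseline covariate would then explain part of the between-subject variation and correct for chance imbalance between arms. The plan accepts this for its three CLUE domain scores but not for the one CLUE item among the primary endpoints. Because all five primary hypotheses must succeed, a wide interval here can fail the whole primary objective even when the lenses are equal. At stake is the chance of passing, not the validity of the comparison.

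**Working it through.** **The plan's own figure.** SAP Table 11 gives 40 subjects and 87% power for this endpoint. Drawing from the SAP Table 10 rates with independent arms, 40 per arm gives 58% (one-sided 2.5%) or 70% (one-sided 5%) against the odds-ratio margin of 0.67, and 77% or 85% against the -0.10 margin. Some paired settings also come close to 87%. The subject-level crossover data behind the SAP's bootstrap are not shown, so the figure is neither reproduced nor called wrong. The rest of the check does not depend on it.

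**Inputs.**
- Historical top-two-box rates (SAP Table 10): Test (72 + 129)/242 = 83.1%; Control (51 + 130)/242 = 74.8%; difference 8.3 points.
- 112 completers per arm (SAP 2.3).
- Rule: lower 95% limit of p_T - p_C above -0.10 (SAP 10.1).
- A no-difference case and a 50% reference rate, both named in SAP 7.4. The five-category split at 50% is assumed.
- Correlation r between baseline and the scale underlying the follow-up rating: assumed 0.3 and 0.5.

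**Method.** Simulated trials, 1,000 to 3,000 per setting, were fitted by proportional-odds maximum likelihood as a stand-in for the vague-prior Bayesian model. In the adjusted analysis, p_T - p_C was averaged over observed baseline values.

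| True rates, Test vs Control | SE without baseline | SE, r = 0.3 | SE, r = 0.5 | Power without baseline | Power, r = 0.3 | Power, r = 0.5 |
|---|---|---|---|---|---|---|
| 75% vs 75% | 0.048 | 0.045 | 0.042 | 57% | 60% | 68% |
| 50% vs 50% | 0.060 | 0.056 | 0.050 | 38% | 43% | 50% |
| 83% vs 75% | 0.042 | 0.041 | 0.038 | 99% | 99.7% or more | 99.7% or more |

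In the first row the SE falls by 0.003/0.048 = 6% and 0.006/0.048 = 12.5%. Repeat runs moved the adjusted powers in that row by up to about 3 points.

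**Check by hand.** Power is approximately Φ((d + 0.10)/SE - 1.96), where d is the true difference.
- 75% vs 75%: Φ(0.10/0.048 - 1.96) = Φ(0.12) = 55%; with SE 0.045, Φ(0.26) = 60%; with SE 0.042, Φ(0.42) = 66%.
- 50% vs 50%: Φ(0.10/0.060 - 1.96) = Φ(-0.29) = 39%; with SE 0.050, Φ(0.04) = 52%.
- 83% vs 75%: Φ(0.183/0.042 - 1.96) = Φ(2.40) = 99%.

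These agree with the simulation to within about 2 points.

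**Where the gain comes from.** On the log-odds-ratio scale there is none. At the 75% rate the SE of the lens coefficient rises from 0.255 to about 0.262 at r = 0.5. Against the 0.67 margin, |ln 0.67| = 0.400, so power is Φ(0.400/0.255 - 1.96) = 35% without baseline and Φ(0.400/0.262 - 1.96) = 33% with it.

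A plug-in at mean baseline gives no reliable gain either. With no difference at 75%, power went from 57% to 59% (r = 0.3) and from 55% to 64% (r = 0.5). At 50% it went from 38% to 39% and from 39% to 38%. Such a plug-in also describes a subject at average baseline, whereas the hypothesis concerns the group proportions.

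**The case against.** The strongest reply is that this is a preference, not an error. The unadjusted randomised comparison is valid, age and sex are already in the code, and at the historical rates the test passes about 99% of the time either way. All of that stands. It limits the point to efficiency and makes its value depend on the true effect. The no-difference case is still fair to examine, because SAP 7.4 uses it when converting the margin.

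A second reply is that the inputs are uncertain. The documents give no correlation. Baseline ratings refer to assorted habitual lenses, and their link to one item about a photochromic lens is unknown. That also stands, and it is why a range is shown.

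A third is that a baseline vision score is not shown to exist. The questionnaire appendix is not visible, and the code reused for the secondary endpoints defines its baseline variable only as the comfort score. SAP 10.2 can be carried out as written only if a vision baseline is available, which is a strong inference but not a statement.

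A reader might infer that the residual variance falls by r², that is 9% to 25%, as soon as the covariate is added. That is the linear-model rule and does not carry over to the cumulative-logit lens coefficient. Nor should the gain be judged against the odds ratio of 0.67. That margin appears only in the sample-size text, and at a 74.8% Control rate it is stricter than the decision rule: odds 0.748/0.252 = 2.97, times 0.67 = 1.99, proportion 66.5%, a drop of 8.3 points instead of 10.

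**Conclusion.** The point holds as an avoidable loss of efficiency on a must-pass endpoint. With no true difference at the 75% Control rate, adjusting and averaging would raise power from about 57% to about 60% (r = 0.3) or 68% (r = 0.5). With the historical advantage the gain is negligible. These figures rest on the assumed correlations, proportional odds, maximum likelihood in place of the Bayesian fit, and a usable baseline score.

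A reader might go further and conclude that the planned analysis is biased, or that the endpoint is underpowered whatever the true effect. The documents support neither: randomisation protects the unadjusted comparison, and the low power appears only if Test has no advantage.

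**What to change.** 1. Confirm that the baseline questionnaire yields a CLUE Overall Quality of Vision score, or item V015_1 itself. State in SAP 14.2 which baseline variable each secondary CLUE model uses.
2. Before database lock, prespecify that baseline measure, centred, as a covariate in the ordinal model in both SAP 10.1 and the code.
3. Replace the plug-in probabilities. At each posterior draw, predict every analysed subject's probability of agreeing or strongly agreeing under Test and under Control, average each over subjects, and take the difference. State how the site effect enters. This also removes the evaluation at age zero that the displayed code implies if age is uncentred. An uncentred baseline score would have the same fault, being evaluated at CLUE 0 when the population mean is 60.
4. Keep the lens-only model as a sensitivity analysis, and say how a missing baseline score is handled, since SAP 7.6 rules out imputation.

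The cost is one covariate and a modest rewrite of the post-processing code. No new data, subjects or visits are needed.

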#### Hypothesis Testing

The null and alternative hypotheses for non-inferiority are as follows:

$$\begin{array}{l} H_0 \ p_T - \ p_C \leq -0.1 \\ H_A \ p_T - \ p_C > -0.1 \end{array}$$

Where  $p_T$  and  $p_C$  are the proportions of patients with positive response (agree or strongly agree) in the Test group and Control group, respectively. Non-inferiority will be declared if the lower bound of the 2-sided 95% credible confidence interval is above -0.1 i.e.  $P(p_T - p_C > -0.1)=0.975$ .

Primary Safety Analysis:

Safety analysis will be conducted on safety population by actual treatment received by subjects.

#### Acceptable Lens Fit:

Acceptable lens fit will be analyzed using a Bayesian beta-binomial models for correlated binary data.

The Model:

Let Y1 and Y2 denote the binary outcomes of acceptable lens fit for the left and right eyes, respectively, when wearing the test lens. Considering the correlation,  $\rho$ , between Y1 and Y2, the distribution of the sum Y = Y1 + Y2 is obtained by the mixture of two variables. One of them follow a binomial distribution Bin(2, p) with mixing probability (1- $\rho$ ) and the other one follows a modified Bernoulli distribution MBern(p), taking value 0 and 2 rather than conventional 0 and 1, with mixing probability p:

 $P(Y = y | p, \rho) = (1 - \rho)Bin(2, p)I_{A1} + \rho MBern(p)I_{A2}$ Where  $I_{A1} = \{0, 1, 2\}$  and  $I_{A2} = \{0, 2\}$ 

To overcome the complexity of the mixture likelihood a latent variable  $Z_i$ , i = 1, 2 is introduced in the model to indicate in which component of the model the observation  $y_i$ , i=1, 2, belongs to, that is,

 $z_i = \begin{cases} 1, \text{if the observation belong to the MBern(p),} \\ 0, \text{if the observation belong to the Bin(2, p)} \end{cases}$ 

The joint distribution of the augmented data (Yi, Zi), i=1, 2, is given by  $P(Y = y_i, Z = z_i | p, \rho) = \rho^{z_i} p^{y_i z_i/2} (1-p)^{(2-y_i)z_i/2} (1-\rho)^{1-z_i} {2 \choose y_i} p^{y_i(1-z_i)} (1-p)^{(2-y_i)(1-z_i)}$ The posterior distribution of (p,  $\rho$ ) given (y, z) is

 $P(\mathbf{p}, \boldsymbol{\rho} \mid \mathbf{z}, \mathbf{y}) = P(\mathbf{y}, \mathbf{z} \mid \mathbf{p}, \boldsymbol{\rho}) \pi_0(\mathbf{p}, \boldsymbol{\rho}),$ 

Where,  $\pi_0$  is joint prior distribution of  $(p, \rho)$ . Here we assume p and  $\rho$  to be independent with a prior beta $(\alpha,\beta)$  for p and uniform(0,1) for  $\rho$ . Hence the joint distribution of  $(p, \rho)$  is given by  $\pi_0$   $(p, \rho | \alpha, \beta) \propto p^{\alpha - 1} (1-p)^{\beta - 1}$ . The Metropolis sampler algorithm as implemented in the SAS/STAT MCMC Procedure will be used to estimate the posterior distributions of the parameters  $(p, \rho)$ . Inferences will be made based on a posterior credible interval for the relevant parameters.

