## 4. STATISTICAL HYPOTHESES FOR STUDY OBJECTIVES

#### 4.1. Primary Hypotheses

All the primary hypotheses must be met in order to satisfy the primary objective of this study.

- 1. Subjects wearing the JJVCI Investigational contact lenses on a daily wear basis will have patient reported comfort at the 2-Week Follow Up visit that is non-inferior to that of subjects wearing predicate device on a daily wear basis. A non-inferiority margin of -5 CLUE points will be used.
- 2. Subjects wearing the JJVC Investigational contact lenses on a daily wear basis will report distance monocular visual acuity (logMAR: bright room luminance / high contrast charts) at the 2-Week Follow Up visit that is non-inferior to that of subjects wearing predicate device on a daily wear basis. A non-inferiority margin of 0.05 LogMAR will be used.
- 3. Subjects wearing the JJVCI Investigational contact lenses on a daily wear basis will have patient reported outcome (Agree and Strongly Agree) on the Quality of Vision in Bright Light at the 2-Week Follow Up visit that is non-inferior to that of subjects wearing predicate device on a daily wear basis. A non-inferiority margin of 10% will be used.
- 4. Subjects wearing the JJVC Investigational contact lenses on a daily wear basis will have a percentage of any grade 3 or higher slit lamp findings at all visits (scheduled and unscheduled) that is non-inferior to that of subjects wearing predicate device on a daily wear basis. A non-inferiority margin of 5% will be used.
- 5. At least 90% of eyes wearing the JJVC Investigational contact lenses on a daily wear basis will have acceptable fits across the fitting and follow-up visits.

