#### **Hypothesis Testing**

With respect to Acceptable lens fit the null and alternative hypothesis for superiority is as follows:

$$H_o: p_T \le 0.90$$
  
 $H_A: p_T > 0.90$ 

Where,  $p_T$  represents the proportion of subject eyes that achieve acceptable fit for the Test lens. Success for acceptable fit will be declared if the lower bound of the 2-sided 95% credible interval of the proportion is greater than 0.90; i.e.  $P(p_T > 0.90) \ge .975$ . If the full planned model fails to converge, reduced versions may be considered.

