# Where,

ads\_VS =analysis data set for Vision Satisfaction in Bright Lighting trtan= numerical representation of treatment, where Test=1 and Control=0

```
CR-6305, Statistical Analysis Plan Version 1.0
```

age= Age of subject at time of consent sexn= Numerical representation of sex, where Female=1 and Male=0; siteid= Site Number

Lens Fit

```
PROC MCMC DATA=ads_LF DIC MCHISTORY=brief

NBI=50000 NMC=200000 THIN = 50 STATS=ALL plots(smooth) MONITOR=(_parms_)

OUTPOST =post STATS(ALPHA=(0.05) PERCENTAGE=(2.5 25 50 75 97.5) ) SEED=53457 ;

ODS OUTPUT PostSummaries = PostSummaries ;

ODS OUTPUT PostIntervals = PostIntervals ;

BY trta;

PARM p 0.5 ;

PARM ro .6 ;

PRIOR ro ~uniform(0,1);

PRIOR p ~ beta(0.5, 0.5);

;

llike = log( (1-ro)*PDF('BINOMIAL', y, p, 2) + z*ro*(PDF('BINOMIAL',y,p,2)**0.5));

MODEL y ~ GENERAL(llike);

RUN;

Slit lamp Findings (Grade 3 or higher)
```

```
PROC MCMC DATA=ads SLF DIC MCHISTORY=brief

NBI=100000 NMC=500000 THIN =100 STATS=ALL plots(smooth) MONITOR=(_parms_

P C P T)

OUTPOST =post STATS(ALPHA=(0.05) PERCENTAGE=(2.5 25 50 75 97.5)) SEED=53457 ;

ODS OUTPUT PostSummaries = PostSummaries ;

ODS OUTPUT PostIntervals = PostIntervals ;

PARMS (beta0 beta1 beta2 beta3) 0 sigma_site 1 sigma_subject 1;

PRIOR beta: ~NORMAL(0, var=1000);

PRIOR sigma_site~ IGAMMA(shape=0.01, scale=0.01);

PRIOR sigma_subject ~UNIFORM(0,100);
```

```
RANDOM gamma site ~NORMAL(0, var=sigma site) SUBJECT=siteid;
RANDOM gamma_subject ~NORMAL(0, sd=sigma_subject) SUBJECT=site_subjid;
```

 $mu = beta0 + beta1*trtan + beta2*age + beta3*sexn + gamma_site + gamma_subject;$ 

p = logistic(mu);

MODEL  $y \sim BINARY(P);$ 

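### The augmented lens-fit density in SAP 10.1 omits the {0,2} restriction, and the SAP 14.1 program multiplies the correlated term by a z that is never defined

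*SAP*

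**What the plan says.** Lens fit is one of five primary hypotheses that must all be met. SAP 4.1 states it as "At least 90% of eyes wearing the JJVC Investigational contact lenses on a daily wear basis will have acceptable fits", and SAP 10.1 gives the rule: "Success for acceptable fit will be declared if the lower bound of the 2-sided 95% credible interval" of the proportion exceeds 0.90, that is, P(p>0.90) ≥ 0.975.

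SAP 10.1 models Y, the number of acceptable eyes per subject, as a mixture. With weight 1−ρ the eyes are independent, Bin(2,p). With weight ρ they agree completely, MBern(p), described as "taking value 0 and 2 rather than conventional 0 and 1". The marginal line "1 - \rho)Bin(2, p)I_{A1} + \rho MBern(p)I_{A2" carries the supports {0,1,2} and {0,2}.

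The SAP continues: "To overcome the complexity of the mixture likelihood a latent variable" z, equal to 1 if the observation belongs to MBern and 0 if it belongs to Bin. The joint density that follows contains "p^{y_i z_i/2} (1-p)^{(2-y_i)z_i/2". It has no support indicator, and its binomial coefficient is not confined to the z=0 term. Protocol 14.5 prints the same expression.

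The Lens Fit program in SAP 14.1 sets "PRIOR p ~ beta(0.5, 0.5") for p and a uniform(0,1) prior for ρ. Its log-likelihood is the log of (1−ro) times the binomial probability plus z times ro times the square root of that probability. There is no PARM, PRIOR, RANDOM statement or assignment for z. The Lens Fit block also lacks the list of variable definitions that follows each of the other primary programs.

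**The concern.** A joint density for (y, z) should sum over z to the marginal mixture. The printed one does not, because it gives weight to a state that the SAP has just said cannot occur: one eye acceptable and one not, under complete agreement.

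The program might have settled the matter, since it works from the marginal form. But it needs a value for z on every record, and the documents do not supply one. The text's z is unobserved and so cannot be a data column. The z that would make the code right is a function of y, which is a different quantity. A programmer must therefore choose. The choices do not all give the same posterior for p, and that posterior decides a must-pass endpoint. SAP 1 says the SAP overrides the protocol's statistical section, so no other text resolves it.

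**Working it through.** **The plan's own figure.** SAP 7.4 gives 82% power for fit with n=100 by an exact binomial test against 0.90. The smallest passing count is 96 of 100 (exact one-sided level 0.0237). The alternative rate is not stated. Assumed rates of 0.95, 0.96, 0.97, 0.975 and 0.98 give 43.6%, 62.9%, 81.8%, 89.4% and 94.9%, so 82% is recovered only if 0.97 was assumed. This point does not dispute that figure.

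**The printed density, cell by cell.**
- z=0: (1−ρ)Bin(2,p) for y=0, 1, 2. Correct.
- z=1, y=0: ρ(1−p). z=1, y=2: ρp. Both correct.
- z=1, y=1: 2ρ√(p(1−p)). It should be 0.

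The total is 1 + 2ρ√(p(1−p)). At p=0.95, ρ=0.5 this is 1 + √0.0475 = 1.22. The missing indicator is the cause; the binomial coefficient contributes only the factor 2, since without it the cell would still be ρ√(p(1−p)).

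**The program.** The square root of Bin(2,p) is 1−p at y=0, p at y=2 and √(2p(1−p)) at y=1. The second term is therefore MBern only if it is switched off at y=1:
- z=1 for y in {0,2} and z=0 for y=1: equals the marginal mixture.
- z=1 on every record: adds ρ√(2p(1−p)) at y=1. At p=0.90 the correlated component sums to 1 + √0.18 = 1.42.
- z=0 on every record: the correlated term vanishes. With k unacceptable eyes among 224, p has posterior Beta(224−k+0.5, k+0.5), as if all eyes were independent.
- z absent from the data set: the log-likelihood would probably be missing and the run would stop. This was not tested, as SAS was not available.

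**Effect on the decision.** Inputs: 112 Test completers (SAP 2.3), the priors in SAP 14.1, and the rule in SAP 10.1. The posterior of (p, ρ) was computed on a grid. Entries are P(p>0.90).

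| One-eye / two-eye failures | Correct mixture | z=1 throughout | Printed density | z=0 throughout |
|---|---|---|---|---|
| 0 / 0 | 1.000 pass | 1.000 pass | 1.000 pass | 1.000 pass |
| 11 / 0 | 0.992 pass | 0.980 pass | 0.980 pass | 0.997 pass |
| 12 / 0 | 0.985 pass | 0.968 fail | 0.968 fail | 0.994 pass |
| 13 / 0 | 0.974 fail | 0.951 fail | 0.951 fail | 0.987 pass |
| 0 / 6 | 0.972 fail | 0.972 fail | 0.972 fail | 0.994 pass |

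Under z=0, 14 one-eye failures still pass: Beta(210.5, 14.5) puts 0.9752 above 0.90. In the 12 / 0 row the lower limit is 0.905 for the correct mixture and 0.897 for z=1 or the printed density. The posterior mean of ρ is 0.11 for the correct mixture and 0.94 for the printed density, although no subject failed in both eyes.

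**Chance of passing**, summed exactly over the three outcomes per subject. The true p and ρ are assumptions; the documents give no between-eye correlation for fit.

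| True p, ρ | Correct | z=1 | z=0 |
|---|---|---|---|
| 0.90, 0.3 | 1.9% | 1.1% | 5.4% |
| 0.90, 0.7 | 3.4% | 2.3% | 8.2% |
| 0.95, 0.3 | 65.5% | 55.5% | 81.6% |
| 0.97, 0.3 | 96.5% | 93.9% | 99.1% |

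The printed density passes and fails the same data sets as z=1, so its chances are the same.

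**The case against.** The case for leaving the text largely alone has four parts.

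1. The supports are stated just before the augmented formula, and on every allowed (y, z) pair it is exact. A careful reader would carry the indicator forward. That is fair as to intent, but a density meant for computation has to state its own support.

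2. The program does not use the augmented density. It codes the marginal mixture, and z sits exactly where the {0,2} indicator belongs, so a data indicator is the one reading that makes the code coherent. This is probably what was meant. It stands as an inference, not as a specification, because the only definition of z in the SAP says something else.

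3. Setting z=0 throughout would remove the correlation that the model exists to include, and nothing in the SAP asks for it. This stands. The z=0 figures bound the ambiguity; they do not predict what will be run.

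4. The historical studies had no unacceptable fits (SAP 7.4). If the 430 Test subjects in the slit-lamp table are also the denominator for fit, the upper 97.5% limit is 1 − 0.025^(1/430) = 0.85% of subjects, or about 1 of 112. The decision first changes at 12 subjects with a one-eye failure or 6 with a two-eye failure. This stands and limits the practical consequence.

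A reader might infer that the fit model itself is invalid, or that the trial is likely to reach a wrong fit conclusion. The documents support neither: the marginal mixture is right, the augmented density is not what is programmed, and the versions separate only near the boundary.

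**Conclusion.** The point holds as an error in one printed formula and an undefined variable in a primary-endpoint program. The model idea is sound.

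The direction depends on how z is filled in. With z=1 throughout the test is slightly conservative: one fewer one-eye failure is tolerated (11 instead of 12 of 112, with no two-eye failures), and it cannot pass a lens that the correct model fails in the cases examined. With z=0 throughout it is anti-conservative: 14 are tolerated, and false passes at a true rate of 0.90 are 8.2% instead of 3.4% if ρ is 0.7. If z is missing, the likely result is a failed run, and z would then have to be defined after the data are in.

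These sizes rest on 112 Test subjects with both eyes assessed, the SAP 14.1 priors, and assumed values of p and ρ for the operating characteristics. With almost no unacceptable fits all versions pass. The point is therefore a should-fix: the chance of a changed decision is small, but a pre-specified primary analysis should have one executable meaning.

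**What to change.** In SAP 10.1 and protocol 14.5, either delete the latent-variable augmentation and keep the marginal mixture, or set the z=1 term to zero when y=1 and apply the binomial coefficient to the z=0 term only. The change to the coefficient is tidying, since it equals 1 at y=0 and y=2. Deleting the augmentation is simpler, because the program does not use it.

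In SAP 14.1, replace z in the Lens Fit log-likelihood by the expression (y ne 1). Add a list of definitions under that program, as for the other primary endpoints, stating that y is the number of acceptable eyes (0, 1 or 2) and what the indicator does.

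The cost is one formula and one line of code, with no change to data collection, design or sample size. It should be done before database lock, so that the choice is not made with fit results in view.
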